## IV List of derived variables

Variable Label	Definition
BMI	Weight (kg) / ( Height(cm) / 100 ) 
BMI categories	< 20, 20 to <25, 25 to < 30, 30 to < 35, >=35
Age categories	< 20 years, 20 to < 30 years, 30 to < 40 years, >= 40 years
Feeling like a failure	Never = 4, Rarely = 3, Sometimes = 2, Often = 1, Always = 0
Felling down, depressed or hopeless	Never = 4, Rarely = 3, Sometimes = 2, Often = 1, Always = 0
Feeling happy or optimistic about the future	Never = 0, Rarely = 1, Sometimes = 2, Often = 3, Always = 4
Mood Score	The response to the three mood-related questions ("Feeling like a failure", "Felling down, depressed or hopeless" and "Feeling happy or optimistic about the future") is scored from 0 to 4, with 4 representing the most positive mental state. The scores of the responses to the three mood questions are then summarized into a single comprehensive Mood Score and transformed to a 0 to 100-point scale. A higher score indicates a better mood. Missing scores for a single mood question are replaced by last observation carried forward (LOCF).
Time since first endometriosis symptoms	< 6 months, 6 months to < 1 year, 1 to < 2 years, 2 to < 5 years, 5 to < 10 years, >= 10 years
Time since first diagnosis of endometriosis	< 6 months, 6 months to < 1 year, 1 to < 2 years, 2 to < 5 years, 5 to < 10 years, >= 10 years
Time span between first endometriosis symptoms and diagnosis	< 6 months, 6 months to < 1 year, 1 to < 2 years, 2 to < 5 years, 5 to < 10 years, >= 10 years
Pain severity score	0 to 3 (mild), 4 to 7 (moderate), 8 to 10 (severe)

Supporting document SOP BMT 01.09 – Doc 5002.02 – Effective date 21.03.2017

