6. BASELINE SURVEY

Each physician's office will be provided with simple case report forms (questionnaires) for collecting data at baseline. The baseline visit will take place at the participating physician's office. All women who receive a new prescription for the treatment of endometriosis are to be asked if they are willing to participate. Only after the endometriosis medication has been prescribed will the physician discuss the study with the subject. This ensures that participation in the study is not considered a requirement for treatment. After discussing the study details (including follow-up procedures and intervals, content and duration of follow-up contacts, use of data collected, etc.), each subject will be asked to provide written informed consent to

participate in the study. If the subject needs time to consider participation, she will be permitted to leave the physician's office with her prescription and take an appropriate period to decide whether to participate.

The informed consent will include permission for study data to be collected and analyzed and for contacts to be made by the study team at intervals during the follow-up phase for collection of study information. Each subject will also be asked to provide information regarding alternative contacts (a close relative or friend, or primary care physician) if the study team cannot reach the subject after several attempts. Permission for the study team to contact a subject's primary care physician/ attending physician(s) and to review relevant source data (e.g., medical reports for validation of reported serious clinical outcomes) will also be sought. Follow-up frequency by the study team will be explained, and the content of follow-up contacts will be described.

Confidentiality will be maintained throughout the study and no personal information will be shared with alternative contacts. The funder - Bayer Schering Pharma AG - will not have access to names, addresses, or alternative contact information for the subjects and all individual subject data will remain anonymous. Personal and medical information will be recorded on separate documents. ZEG will ensure that access to personal information is restricted in accordance with data privacy rules.

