#### 3. Study Design

This is a large, prospective, controlled, non-interventional, long-term cohort study which follows two cohorts, users of DNG and users of other medications used for the treatment of endometriosis. The cohorts consist of new users (starter and restarter) or switcher of a hormonal endometriosis treatment. A "non-interference" approach will be used to provide standardized, comprehensive, reliable information on endometriosis treatment patterns.

A follow-up assessment for each woman is scheduled 6, 12, 24, 36 and depending on the date of enrollment 48, 60, 72 and 84 months after baseline. Women will be followed-up for at least 2 years. Women recruited in the early phase of the study will be followed-up until study endpoint [max. 7 years]. By means of these contacts, almost all relevant clinical outcomes will be captured.

However, during the first year of the study, less than 15% of the planned recruitment target within that time frame was achieved (i.e. 1,191 women were recruited rather than the anticipated 8,334 women). As a consequence, the overall recruitment phase was longer (and therefore the observation time was less) than we had expected. In order to achieve the envisaged total observation time of 84,000 women years, the follow-up period will be prolonged by one year (until end of QII 2018).

All clinically relevant serious adverse events will be verified by ZEG through contact with the relevant physicians and by reviewing pertinent source documentation. A standard algorithm will be used to classify 'clinically relevant depression' and 'medically treated anemia' as 'confirmed' or 'not confirmed'. At the end of the study, this classification will be verified by blinded independent adjudication

treatment with GnRH, an estrogen and/or a progestogen (add-back therapy) will be considered as a single treatment regimen. In cases where add-back therapy is used the predefined end-point is the cessation of the add-back therapy.

 Users of non-approved hormonal medications prescribed for endometriosis treatment are additionally followed up and included in the analysis.

 First ever user of EMT

 EMT use after intake break (>= 4 weeks)

 Switching from another EMT

 According Study Protocol, Amendment of September 30, 2017

Supporting document SOP BMT 01.09 - Doc 5002.02 - Effective date 21.03.2017

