#### 5.5 Missing data

The investigators were instructed to obtain complete information on primary and secondary outcome variables and primary risk factors. In case of missing data, numbers will be presented in the respective table categories in the descriptive analysis. However, for certain variables (e.g. Mood Score), the last value is carried forward to replace missing items and calculate the related score (as defined in Appendix IV).

Women with multiple exposure or unspecific treatment will be specified as "Allocation unknown".

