#### Section B – Population Characteristics

Section B summarizes population characteristics of the participating women derived from baseline and follow-up data. The analysis is stratified by country, EMT user type and diagnosis classification.

Section B-1 Age, height, weight and BMI

Section B-2 Socio-economic characteristics and lifestyle factors

Smoking, education level

Supporting document SOP BMT 01.09 - Doc 5002.02 - Effective date 21.03.2017

Section B-3 Gynecological history

Age at menarche, pregnancies, live births, miscarriages, abortions

and/or stillbirths

Section B-4 Endometriosis characteristics

History of EMT use, time since first diagnosis/ first symptoms, surgical procedures,

endometriosis symptoms

Section B-5 Medical History.

Family history of Anemia, Depression,

History of VTE/ATE

Self-reported history of selected cardiovascular risk factors, treated depression and

diseases, presence of mood symptoms

Section B-6 Medication

Regular use of medication, previous medication

Section B-7 Characteristics of Visanne long-term user, Baseline, and Follow-up

Regional distribution, diagnosis classification, age, BMI, endometriosis symptoms

Section B-8 Follow-up characteristics

Mood symptoms and change to baseline, frequencies and timespan of the first switch

after baseline prescription.

Section B-9 Summary tables of selected baseline characteristics

Frequencies of selected baseline characteristics, additionally shown by age categories

and age-standardized and for women with treatment failure and women who

stopped/switched their treatment

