Table B-8.9.13	Mood symptoms at 84 months after study entry, AT population, Ukraine

Supporting document SOP BMT 01.09 – Doc 5002.02 – Effective date 21.03.2017

Section B-8.10 Change of Mood Score after study entry, constant user only

Table B-8.10.1 Change of Mood Score after study entry, constant user only\*, AT population, Complete cohort

	DNG		OAED			NAED	Allocation unknown	Total	
		GnRH-a	Danazol	All OAED	СС	Other progestin	All NAED		
Number (%) of women	xx ( 100%)	xx ( 100%)	xx ( 100%)	xx ( 100%)					
Change of Mood Score**									
N									
Mean (± SD)									
Change from Baseline to 6	xx	xx	xx	xx	xx	xx	xx	xx	xx
months follow up	xx.x (± xx.xx)	xx.x (± xx.xx)	xx.x (± xx.xx)	xx.x (± xx.xx)					
Change from Baseline to 12	xx	xx	XX	xx	XX	xx	xx	XX	xx
months follow up	xx.x (± xx.xx)	xx.x (± xx.xx)	xx.x (± xx.xx)	xx.x (± xx.xx)					
Change from Baseline to 24	XX	XX	XX	xx	xx	xx	xx	XX	xx
months follow up	xx.x (± xx.xx)	xx.x (± xx.xx)	xx.x (± xx.xx)	xx.x (± xx.xx)					
Change from Baseline to 36	xx	xx	XX	xx	XX	xx	xx	XX	xx
months follow up	xx.x (± xx.xx)	xx.x (± xx.xx)	xx.x (± xx.xx)	xx.x (± xx.xx)					
Change from Baseline to 48	XX	XX	XX	xx	XX	xx	XX	XX	xx
months follow up	xx.x (± xx.xx)	xx.x (± xx.xx)	xx.x (± xx.xx)	xx.x (± xx.xx)					
Change from Baseline to 60	xx	xx	XX	xx	XX	xx	xx	XX	xx
months follow up	xx.x (± xx.xx)	xx.x (± xx.xx)	xx.x (± xx.xx)	xx.x (± xx.xx)					
Change from Baseline to 72	xx	xx	XX	xx	XX	xx	xx	XX	xx
months follow up	xx.x (± xx.xx)	xx.x (± xx.xx)	xx.x (± xx.xx)	xx.x (± xx.xx)					
Change from Baseline to 84	xx	xx	xx	xx	XX	xx	xx	xx	xx
months follow up	xx.x (± xx.xx)	xx.x (± xx.xx)	xx.x (± xx.xx)	xx.x (± xx.xx)					

Note:\* Only women who continuously used their baseline prescription are considered

Supporting document SOP BMT 01.09 – Doc 5002.02 – Effective date 21.03.2017

Note: \*\* Mood score is calculated as described in the SAP Appendix IV.

Date of analysis:

Table B-8.10.2	Change of Mood Score after study entry, constant user only*, AT population, Starter
Table B-8.10.3	Change of Mood Score after study entry, constant user only *, AT population, Switcher
Table B-8.10.4	Change of Mood Score after study entry, constant user only *, AT population, Restarter
Table B-8.10.5	Change of Mood Score after study entry, constant user only *, AT population, Diagnosis confirmed by surgery
Table B-8.10.6	Change of Mood Score after study entry, constant user only *, AT population, Diagnosis based on clinical symptoms

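### A missing mood item is filled with an answer nominally 6 to 12 months old: its change is forced to zero at month 6, and later scores are pulled toward the previous visit

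*SAP*

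**What the plan says.** SAP Appendix IV defines the Mood Score from three questions, each "scored from 0 to 4, with 4 representing the most positive mental state". They are added and "transformed to a 0 to 100-point scale". For blanks the appendix states: "Missing scores for a single mood question are replaced by last observation carried forward (LOCF". Section 5.5 gives the same rule for variables such as this one: "the last value is carried forward to replace missing items and calculate the related score". Neither place limits the age of the carried answer, says what happens when two or three items are blank or when the blank is at baseline, or plans an analysis without the carried values.

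Follow-up is "scheduled 6, 12, 24, 36 and depending on the date of enrollment 48, 60, 72 and 84 months after baseline" (SAP section 3). The entry answer is collected around the time of the new prescription. Protocol section 6 states: "Only after the endometriosis medication has been prescribed will the physician discuss the study with the subject".

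The SAP places mood among the follow-up characteristics (section 8, Section B): "Mood symptoms and change to baseline, frequencies and timespan of the first switch". Tables B-8.1 to B-8.9 show the items and the score at each visit, with women allocated by the treatment they are using at that time. Tables B-8.10 and B-8.11 show mean change from baseline. The note to B-8.10 reads: "Only women who continuously used their baseline prescription are considered". B-8.11 covers the first treatment episode of women who switched or stopped.

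**The concern.** The follow-up mood questions ask about the last 4 weeks (SAP Appendix II). Carrying an answer forward replaces that window with one from a questionnaire 6 or 12 months earlier, or older still if the item was also blank then. The two answers the woman did give at the visit play no part in filling the gap.

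Two consequences follow.

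- **At month 6** the only earlier answer is the one from study entry, so the item shows no change whatever happened to the woman's mood.
- **In the tables allocated by current treatment** (B-8.2 onward) the carried answer may have been given on a different drug, yet it is counted under the present one. SAP section 5.1 takes the opposite approach for outcomes, which are assigned to the treatment in use when they occurred.

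Mood disturbance is part of the study's rationale (Protocol section 1), and Tables B-8.10 and B-8.11 are where mood change is reported. The accuracy of that description is what is at stake.

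**Working it through.** The documents give no effect size, power or missingness figure for the Mood Score, so there is no stated number to reproduce. The check is direct arithmetic on the scoring rule.

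**Inputs.** Three items scored 0 to 4, summed to 0 to 12 and rescaled to 0 to 100 (Appendix IV). Visits at 0, 6, 12, 24 months and so on (section 3). The share m of women with one missing item at a visit is not given and is assumed to lie between 2% and 30%.

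**Scale.** Score = sum × 100/12. One response step on one item is 100/12 = 8.3 points, and each item carries one third of the score.

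**One woman at month 6.** Suppose she answers 3, 3, 3 at entry and her true state at month 6 is 2, 2, 2.
- True change: −3 × 100/12 = −25.0.
- With one item carried from entry (3, 2, 2): −2 × 100/12 = −16.7. One third is lost.

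**Cohort mean.** Let D_k be the true mean change from baseline at visit k, with D_0 = 0. Assume that items change equally and blanks are unrelated to mood. A woman with one carried item contributes (2/3)D_k + (1/3)D_(k−1). The observed mean is therefore

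D_k − (m/3)(D_k − D_(k−1)).

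At month 6 this is D × (1 − m/3):

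| m | Shrinkage of month-6 mean change (m/3) |
|---|---|
| 2% | 0.7% |
| 5% | 1.7% |
| 10% | 3.3% |
| 20% | 6.7% |
| 30% | 10.0% |

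**Unequal missingness.** With a true change of −10 in two cohorts and m of 20% and 5%, the observed means are −10 × (1 − 0.20/3) = −9.33 and −10 × (1 − 0.05/3) = −9.83. The rule alone creates a difference of 0.5 points.

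**One woman at month 12, one item carried from month 6.** She starts at 3, 3, 3 and is at 2, 2, 2 at month 6.

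| Course | True month-12 answers | True change | With LOCF | Effect |
|---|---|---|---|---|
| Progressive worsening | 1, 1, 1 | −50.0 | −41.7 | toward zero |
| Sustained worsening | 2, 2, 2 | −25.0 | −25.0 | none |
| Transient worsening | 3, 3, 3 | 0.0 | −8.3 | away from zero |

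After month 6 the pull is thus toward the previous visit's change. It is toward zero with certainty only at month 6, or later if that item was blank at every visit in between.

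**The case against.** The case for leaving the rule alone is substantial.

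- The Mood Score is not a primary or secondary outcome (SAP sections 5.4 and 5.4.4), not a listed covariate (section 5.4.2, Appendix III) and not part of the inferential tables in Section D. No hypothesis or margin depends on it.
- The primary depression outcome rests on a psychiatric specialist's diagnosis or on a suicide or suicide attempt (section 5.4.3). LOCF does not enter it.
- Missing answers are to be queried before data entry (Protocol section 10), so only residual blanks are filled. The item tables also keep a row for missing answers by cohort and visit.
- On an illustrative mean change of 10 points, m of 5 to 10% costs 10 × 1.7% to 10 × 3.3%, or 0.17 to 0.33 points.
- The documents report no correlation between the three items, so scoring from two of them exchanges one untested assumption for another.

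All of this stands, and it sets the size of the point. It does not show that an older answer suits a question about the last 4 weeks. The row of missing answers reveals how often the rule acts but does not remove its effect on the mean. On the last item, the SAP already adds the three questions with equal weight into one score, so treating them as one construct introduces nothing foreign to the plan.

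A reader might go further and infer that the rule biases every mood comparison toward no effect for every drug, or that it could hide a depression signal. The documents do not support either inference. The direction is fixed only at month 6, the m/3 figure applies only there, and depression is measured separately.

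**Conclusion.** The point holds as a minor one. The rule gives a distorted change at month 6 for any woman with a filled item: that item contributes zero, and one third of her score change is lost when the three items moved together. The month-6 cohort mean shrinks by m/3, which is 1.7 to 3.3% for m of 5 to 10% and 0.7 to 10% for m of 2 to 30%. At later visits the distortion can go either way. In the tables allocated by current treatment, the filled answer may belong to a different drug. That problem does not arise between drugs used during follow-up in B-8.10, which is limited to women who stayed on the baseline prescription.

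The figures rest on an assumed m, on items that change equally, and on blanks unrelated to mood. If women in low mood skip items more often, or if missingness differs by cohort, the distortion could be larger. The consequences stay within the descriptive mood tables of Section B-8.

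**What to change.** Replace the LOCF sentence in Appendix IV, and align section 5.5, with the following.

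1. If one item is missing at a visit, score that visit from the two answered items: sum × 100/8.
2. Compute change from baseline on the items answered at both visits, rescaled to 0 to 100.
3. If two or more items are missing, set the score to missing. If the two visits share fewer than two items, set the change to missing.
4. Apply the same rule at baseline.
5. Report how many scores use two items, by cohort and visit, and keep LOCF only as a sensitivity table.

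Step 2 is needed because items may differ in level. As an illustration, take a woman who answers 4, 4, 1 at entry (9 × 100/12 = 75.0), does not change, and leaves the third item blank at month 6. Her two-item score is 8 × 100/8 = 100, an apparent gain of 25.0. On the two shared items the change is 100 − 100 = 0.

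The cost is a few lines of text and one extra table. The downside is the assumption that the missing item moves with the other two. In the month-6 example above, if only the two answered items had worsened, the true change would be −16.7 and the new rule would give −2 × 100/8 = −25.0. The sensitivity table shows how much this matters.

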#### Section A Population Distribution

Section A-1 Eligibility status

Section A-1.1 Eligibility Status (all recruited women)

Table A-1.1.1 Eligibility Status (all recruited women)

	Total
Number (%) of recruited women	xx ( 100%)
Thereof	
Enrolled women	xx ( xx.x%)
Not enrolled women	xx ( xx.x%)
Number (%) of women not enrolled  Reason	xx ( 100%)
Duplicate	xx ( xx.x%)
No complete informed consent available	xx ( xx.x%)
Language problems	xx ( xx.x%)
< <category>></category>	xx ( xx.x%)

Supporting document SOP BMT 01.09 – Doc 5002.02 – Effective date 21.03.2017

#### Section A-1.2 Study status of women at follow-up

Table A-1.2.1 Study status of women at follow-up, ITT population, Complete cohort

	DNG	OAED				NAED	Allocation unknown	Total	
		GnRH-a	Danazol	All OAED	CC	Other progestin	All NAED		
Number (%) of women	xx (100%)	xx ( 100%)	xx ( 100%)	xx ( 100%)	xx ( 100%)				
At study entry  Thereof	xx ( xx.x%)	xx ( xx.x%)	xx ( xx.x%)	xx ( xx.x%)					
Drop out	xx ( xx.x%)	xx ( xx.x%)	xx ( xx.x%)	xx ( xx.x%)					
Loss to follow-up	xx ( xx.x%)	xx ( xx.x%)	xx ( xx.x%)	xx ( xx.x%)					
At < 6 months  Thereof  Drop out  Loss to follow-up	xx ( xx.x%)	xx ( xx.x%)	xx ( xx.x%)	xx ( xx.x%)					
 At 72 months or later 	xx ( xx.x%)	xx ( xx.x%)	xx ( xx.x%)	xx ( xx.x%)					

Note: \*Presented at the end of follow-up only.

Table A-1.2.2 Study status of women at follow-up, AT population, Complete cohort

Supporting document SOP BMT 01.09 – Doc 5002.02 – Effective date 21.03.2017

#### Section A-2 Distribution of women

#### Section A-2.1 Regional distribution

Table A-2.1.1 Study status of women at follow-up, ITT population, Complete cohort

	DNG OAED					NAED	Allocation unknown	Total	
		GnRH-a	Danazol	All OAED	CC	Other progestin	All NAED		
Number (%) of women	xx ( xx.x%)	xx ( xx.x%)	xx ( xx.x%)	xx ( 100%)					
Germany	xx ( xx.x%)	xx ( xx.x%)	xx ( xx.x%)	xx ( 100%)					
Poland	xx ( xx.x%)	xx ( xx.x%)	xx ( xx.x%)	xx ( 100%)					
Russia	xx ( xx.x%)	xx ( xx.x%)	xx ( xx.x%)	xx ( 100%)					
Hungary	xx ( xx.x%)	xx ( xx.x%)	xx ( xx.x%)	xx ( 100%)					
Switzerland	xx ( xx.x%)	xx ( xx.x%)	xx ( xx.x%)	xx ( 100%)					
Ukraine	xx ( xx.x%)	xx ( xx.x%)	xx ( xx.x%)	xx ( 100%)					

Supporting document SOP BMT 01.09 – Doc 5002.02 – Effective date 21.03.2017

#### Section A-2.2 EMT user type at study entry

Table A-2.2.1 EMT user type at study entry, ITT population, Complete cohort

	DNG		OAED			NAED	Allocation unknown	Total	
		GnRH-a	Danazol	All OAED	CC	Other progestin	All NAED		
Number (%) of women	xx ( 100%)	xx ( 100%)	xx ( 100%)	xx ( 100%)					
Starters	xx ( xx.x%)	xx ( xx.x%)	xx ( xx.x%)	xx ( xx.x%)					
Switchers	xx ( xx.x%)	xx ( xx.x%)	xx ( xx.x%)	xx ( xx.x%)					
Restarters	xx ( xx.x%)	xx ( xx.x%)	xx ( xx.x%)	xx ( xx.x%)					

Date of analysis:

Table A-2.2.2 EMT user type at study entry, ITT population, Germany

Table A-2.2.3 EMT user type at study entry, ITT population, Poland

Table A-2.2.4 EMT user type at study entry, ITT population, Hungary

Table A-2.2.5 EMT user type at study entry, ITT population, Switzerland

Table A-2.2.6 EMT user type at study entry, ITT population, Russia

Table A-2.2.7 EMT user type at study entry, ITT population, Ukraine

Supporting document SOP BMT 01.09 - Doc 5002.02 - Effective date 21.03.2017

#### Section A-2.3 Classification of endometriosis diagnosis at study entry

Table A-2.3.1 Classification of endometriosis diagnosis at study entry, ITT population, Complete cohort

DNG	OAED				NAED	Allocation unknown	Total	
	GnRH-a	Danazol	All OAED	CC	Other progestin	All NAED		
xx ( 100%)	xx ( 100%)	xx ( 100%)	xx ( 100%)	xx ( 100%)				
xx ( xx.x%) xx ( xx.x%)	, ,	, ,	xx ( xx.x%) xx ( xx.x%)	xx ( xx.x%) xx ( xx.x%)	xx ( xx.x%) xx ( xx.x%)			
	xx ( 100%) xx ( xx.x%)	GnRH-a  xx ( 100%)	GnRH-a Danazol  xx ( 100%)	GnRH-a         Danazol         All OAED           xx ( 100%)         xx ( 100%)         xx ( 100%)           xx ( xx.x%)         xx ( xx.x%)         xx ( xx.x%)	GnRH-a         Danazol         All OAED         CC           xx ( 100%)         xx ( 100%)         xx ( 100%)         xx ( 100%)           xx ( xx.x%)         xx ( xx.x%)         xx ( xx.x%)         xx ( xx.x%)	GnRH-a         Danazol         All OAED         CC         Other progestin           xx ( 100%)         xx ( 100%)	GnRH-a         Danazol         All OAED         CC         Other progestin         All NAED           xx ( 100%)         xx	DNG         OAED         NAED         unknown           GnRH-a         Danazol         All OAED         CC         Other progestin         All NAED           xx (100%)         xx (100%)

Date of analysis:

Table A-2.3.2	Classification of endometriosis diagnosis at study entry, ITT population, Starter
---------------	-----------------------------------------------------------------------------------

 Table A-2.3.3
 Classification of endometriosis diagnosis at study entry, ITT population, ITT, Switcher

Table A-2.3.4 Classification of endometriosis diagnosis at study entry, ITT population, Restarter

Table A-2.3.5 Classification of endometriosis diagnosis at study entry, ITT population, Germany

Table A-2.3.6 Classification of endometriosis diagnosis at study entry, ITT population, Poland

Table A-2.3.7 Classification of endometriosis diagnosis at study entry, ITT population, Hungary

Table A-2.3.8 Classification of endometriosis diagnosis at study entry, ITT population, Switzerland

Table A-2.3.9 Classification of endometriosis diagnosis at study entry, ITT population, Russia

Table A-2.3.10 Classification of endometriosis diagnosis at study entry, ITT population, Ukraine

Supporting document SOP BMT 01.09 - Doc 5002.02 - Effective date 21.03.2017

